6.3.6 Physical examination

The timing of individual examinations is indicated in the Study Plan ([Table 1](#)). A complete physical examination will be performed at screening and follow-up and include an assessment of the following: general appearance, skin, head and neck, lymph nodes, thyroid, abdomen, musculoskeletal, cardiovascular, respiratory and neurological systems.

Height will be measured in centimetres and weight in kilograms in underwear. Measurements should be taken without shoes and the same scale used for all measurements. BMI will be calculated from the height and weight.

A medical history will be recorded at the Screening visit only.

6.3.7 Resting ECG

An ECG recording will be performed as described in [Table 1](#) and [Table 2](#).

The ECG will be recorded at a paper speed of 25 mm/s and a standard calibration of 1 mV (= 10 mm) for each lead with a standard digital ECG and a Cardiosoft® (CS) version 6.51 ECG device, manufactured by General Electrics Medical Systems (GEMS, Freiburg, Germany).

The 12-lead ECGs will be recorded after the healthy volunteers have rested for at least 10 minutes in supine position. Six limb leads, as specified by Einthoven (I, II and III) and Goldberger (aVR, aVL, aVF), and six pre-cordial leads (V1–V6), according to Wilson, will be used.

Each ECG will include the following information: identification of each lead, study number, subject number, paper speed, voltage calibration as well as date and time of the recording. After conduction, the ECGs will be stored electronically in the CS database and the parameters may be exported to other databases.

The parameters HR, RR, PQ, QRS, QT and QTcB calculated by the Bazett formula ($QTc = QT/RR^{0.5}$) will be assessed. ECG recordings will capture at least four QRS complexes, i.e. three evaluable RR intervals. All ECG data are captured and assessed electronically.

The investigator or a designate will evaluate whether the ECG is normal or abnormal and whether it is clinically significant, if abnormal.

ECGs may be repeated for quality reasons and the repeat used for analysis. Additional ECGs may be collected by the Investigator for safety reasons. Clinically relevant abnormal findings will be reported as adverse events.

6.3.8 Vital signs

6.3.8.1 Pulse and blood pressure

Supine blood pressure and pulse rate will be measured using an oscillometric BP rate monitor (Dynamap Pro Care®), manufactured by General Electrics Medical Systems (GEMS) after 10 minutes rest on a bed. Pulse will be recorded simultaneously with the BP measurements by the same monitor. For timings of assessments refer to the Study Plans [Table 1](#) and [Table 2](#).

6.3.8.2 Body temperature

Oral body temperature will be measured for at least one minute using a digital thermometer (DIGItmp[®], LDM Pharma, Wesel, Germany) at the times indicated in the Study Plans [Table 1](#) and [Table 2](#).

6.3.9 Other safety assessments

No further safety assessments will be performed.

6.4 Pharmacokinetics

6.4.1 Collection of samples

Blood samples for determination of dapagliflozin (4 mL) and metformin (2 mL) in plasma will be taken at the times presented in the study plan [Table 2](#).

Samples will be collected, labelled stored and shipped as detailed in Laboratory Manual.

For blood volume see section [7.1](#).

6.4.2 Determination of drug concentration

Samples for determination of concentration of dapagliflozin in plasma will be analysed using appropriate bioanalytical methods on behalf of Clinical Pharmacology & DMPK, AstraZeneca, Mölndal, by Atlanbio, France. Full details of the analytical methods used will be described in a separate bioanalytical report. Samples for determination of concentration of metformin in plasma will be analysed using appropriate bioanalytical methods on behalf of Clinical Pharmacology & DMPK, AstraZeneca, Mölndal, Sweden, by Atlanbio. Full details of the analytical methods used will be described in a separate bioanalytical report.

7. BIOLOGICAL SAMPLING PROCEDURES

7.1 Volume of blood

The total volume of blood that will be drawn from each healthy volunteer in this study is as follows:

Table 4 Volume of blood to be drawn from each healthy volunteer

Assessment		Sample volume (mL)	No. of samples	Total volume (mL)
Safety	Clinical chemistry	7.5	6	30.0
	Haematology	2.7	6	16.2
	Serology	2.6	1	2.6
	Tricyclic antidepressants	1.1	3	3.3
Pharmacokinetic		6.0	42	252

Table 4 **Volume of blood to be drawn from each healthy volunteer**

Assessment		Sample volume (mL)	No. of samples	Total volume (mL)
Safety	Clinical chemistry	7.5	6	30.0
	Haematology	2.7	6	16.2
	Serology	2.6	1	2.6
	Tricyclic antidepressants	1.1	3	3.3
Total				303.1

Pregnancy and follicle stimulating hormone will be determined within the sample for clinical chemistry.

The number of samples taken, as well as the volume required for each analysis, may be changed during the study as new data on dapagliflozin become available. However, the maximum volume to be drawn from each healthy volunteer will not exceed 450 mL, ie, the same volume as would be drawn during a regular blood donation.

7.2 Handling, storage and destruction of biological samples

The samples will be used up or disposed of after analyses or retained for further use as described here.

7.2.1 Pharmacokinetic and safety samples

Samples will be disposed of after the clinical study report has been finalised.

Blood and urine samples for determination of clinical chemistry, haematology and urinalysis will be disposed of after analysis.

7.3 Labelling and shipment of biohazard samples

The Principal Investigator ensures that samples are labelled and shipped in accordance with the Laboratory Manual and the Biological Substance, Category B Regulations (materials containing or suspected to contain infectious substances that do not meet Category A criteria), see [Appendix C](#) 'IATA 6.2 Guidance Document'.

Any samples identified as Infectious Category A materials are not shipped and no further samples will be taken from the healthy volunteer unless agreed with AstraZeneca and appropriate labelling, shipment and containment provisions are approved.

7.4 Chain of custody of biological samples

A full chain of custody is maintained for all samples throughout their lifecycle. The principal investigator keeps full tractability of collected biological samples from the subjects while in storage at the centre until shipment and keeps documentation of receipt of arrival. The sample receiver keeps full tractability of the samples while in storage and during use until used or

disposed. AstraZeneca or representative keeps oversight of the entire life cycle through internal procedures, monitoring of study sites until samples are used/disposed or transferred for long-term storage, while AstraZeneca performs auditing as applicable of external laboratory providers. Samples retained for further use is registered in AstraZeneca bio bank system during the entire life cycle.

7.5 Withdrawal of informed consent for donated biological samples

If a healthy volunteer withdraws consent to the use of donated biological samples, the samples will be disposed of/destroyed, and the action documented. If samples are already analysed, AstraZeneca is not obliged to destroy the results of this research.

As collection of the biological samples is an integral part of the study, then the healthy volunteer is withdrawn from further study participation.

The Principal Investigator:

- Ensures healthy volunteers' withdrawal of informed consent to the use of donated samples is notified immediately to AstraZeneca.
- Ensures that biological samples from that healthy volunteer, if stored at the study site, are immediately identified, disposed of /destroyed, and the action documented.
- Ensures the laboratory(ies) holding the samples is/are informed about the withdrawn consent immediately and that samples are disposed/destroyed, the action documented and the signed document returned to the study site.
- Ensures that the healthy volunteer and AstraZeneca are informed about the sample disposal.

AstraZeneca ensures the central laboratory(ies) holding the samples is/are informed about the withdrawn consent immediately and that samples are disposed of/destroyed and the action documented and returned to the study site.

8. ETHICAL AND REGULATORY REQUIREMENTS

8.1 Ethical conduct of the study

The study will be performed in accordance with ethical principles that have their origin in the Declaration of Helsinki and are consistent with International Conference on Harmonisation (ICH)/Good Clinical Practice, applicable regulatory requirements and the AstraZeneca policy on Bioethics and Human Biological Samples.

8.2 Subject data protection

The Informed Consent Form will incorporate (or, in some cases, be accompanied by a separate document incorporating) wording that complies with relevant data protection and privacy legislation.

8.3 Ethics and regulatory review

An Ethics Committee should approve the final study protocol, including the final version of the Informed Consent Form and any other written information and/or materials to be provided to the healthy volunteers. The investigator will ensure the distribution of these documents to the applicable Ethics Committee, and to the study site staff.

The opinion of the Ethics Committee should be given in writing. The investigator should submit the written approval to AstraZeneca before enrolment of any healthy volunteer into the study.

The Ethics Committee should approve all advertising used to recruit healthy volunteers for the study.

AstraZeneca should approve any modifications to the Informed Consent Form that are needed to meet local requirements.

If required by local regulations, the protocol should be re-approved by the Ethics Committee annually.

Before enrolment of any healthy volunteer into the study, the final study protocol, including the final version of the Informed Consent Form, is approved by the national regulatory authority or a notification to the national regulatory authority is done, according to local regulations.

AstraZeneca will handle the distribution of any of these documents to the national regulatory authorities.

AstraZeneca will provide Regulatory Authorities, Ethics Committees and Principal Investigators with safety updates/reports according to local requirements, , including Suspected Unexpected Serious Adverse Reactions, where relevant.

8.4 Informed consent

The Principal Investigator will:

- Ensure each healthy volunteer is given full and adequate oral and written information about the nature, purpose, possible risk and benefit of the study.
- Ensure each healthy volunteer is notified that they are free to discontinue from the study at any time.

- Ensure that each healthy volunteer is given the opportunity to ask questions and allowed time to consider the information provided.
- Ensure each healthy volunteer provides signed and dated informed consent before conducting any procedure specifically for the study.
- Ensure that two Informed Consent Forms are signed and one is stored in the Investigator's Study File.
- Ensure a signed Informed Consent Form of the signed Informed Consent Form is given to the healthy volunteer.
- Ensure that any incentives for healthy volunteers who participate in the study as well as any provisions for healthy volunteers harmed as a consequence of study participation are described in the informed consent form that is approved by an Ethics Committee.

8.5 Changes to the protocol and informed consent form

Study procedures will not be changed without the mutual agreement of the Principal Investigator and AstraZeneca.

If there are any substantial changes to the study protocol, then these changes will be documented in a study protocol amendment and where required in a new version of the study protocol (Revised Clinical Study Protocol).

The amendment should be approved by each Ethics Committee and if applicable, also the national regulatory authority, before implementation. Local requirements should be followed for revised protocols.

AstraZeneca will distribute any subsequent amendments and new versions of the protocol to each Principal Investigator(s). For distribution to Ethics Committee see section [8.3](#).

If a protocol amendment requires a change to a centre's Informed Consent Form, AstraZeneca and the centre's Ethics Committee should approve the revised Informed Consent Form before the revised form is used.

If local regulations require, any administrative change will be communicated to or approved by each Ethics Committee.

8.6 Audits and inspections

Authorised representatives of AstraZeneca, a regulatory authority, or an Ethics Committee may perform audits or inspections at the centre, including source data verification. The purpose of an audit or inspection is to systematically and independently examine all study-related activities and documents, to determine whether these activities were conducted, and data were recorded, analysed, and accurately reported according to the protocol, Good Clinical

Practice (GCP), guidelines of the ICH, and any applicable regulatory requirements. The investigator will contact AstraZeneca immediately if contacted by a regulatory agency about an inspection at the centre.

9. STUDY MANAGEMENT BY ASTRAZENECA

9.1 Pre-study activities

Before the first healthy volunteer is entered into the study, it is necessary for a representative of AstraZeneca to visit the investigational study site to:

- Determine the adequacy of the facilities
- Determine availability of appropriate healthy volunteers for the study
- Discuss with the investigator(s) (and other personnel involved with the study) their responsibilities with regard to protocol adherence, and the responsibilities of AstraZeneca or its representatives. This will be documented in a Clinical Study Agreement between AstraZeneca and the investigator.

9.2 Training of study site personnel

Before the first healthy volunteer is entered into the study, an AstraZeneca representative will review and discuss the requirements of the Clinical Study Protocol and related documents with the investigational staff and also train them in any study specific procedures and ClinBase™ system utilised.

The Principal Investigator will ensure that appropriate training relevant to the study is given to all of these staff, and that any new information relevant to the performance of this study is forwarded to the staff involved.

The Principal Investigator will maintain a record of all individuals involved in the study (medical, nursing and other staff).

9.3 Monitoring of the study

During the study, an AstraZeneca representative will have regular contacts with the study site, including visits to:

- Provide information and support to the investigator(s).
- Confirm that facilities remain acceptable.
- Confirm that the investigational team is adhering to the protocol, that data are being accurately and timely recorded in the CRFs, that biological samples are handled in accordance with the Laboratory Manual and that investigational product accountability checks are being performed.

- Perform source data verification (a comparison of the data in the CRFs with the healthy volunteer's medical records at the hospital or practice, and other records relevant to the study) including verification of informed consent of participating healthy volunteers. This will require direct access to all original records for each healthy volunteer (eg, clinic charts).
- Ensure withdrawal of informed consent to the use of the healthy volunteer's biological samples is reported and biological samples are identified and disposed of/destroyed accordingly, and the action is documented, and reported to the healthy volunteer.

The AstraZeneca representative will be available between visits if the investigator(s) or other staff at the centre needs information and advice about the study conduct.

9.3.1 Source data

Source for all data will be presented in a separate Source Data Document, which will be approved and signed by the Principal Investigator before study start.

Electronic CRF (eCRF), EDC application, medical journal and study specific source documents will act as the source data for all information in the study.

9.4 Study agreements

The Principal Investigator should comply with all the terms, conditions, and obligations of the Project Agreement or equivalent for this study. In the event of any inconsistency between this Clinical Study Protocol and the Project Agreement, the terms of Clinical Study Protocol shall prevail with respect to the conduct of the study and the treatment of healthy volunteers. In all other respects, not relating to study conduct or treatment of healthy volunteers, the terms of the Project Agreement shall prevail.

Agreements between AstraZeneca and the Principal Investigator should be in place before any study-related procedures can take place, or healthy volunteers are enrolled.

9.4.1 Archiving of study documents

Study documents will be archived in the Study Master File (SMF) and the Investigator's Study File.

9.5 Study timetable and end of study

The end of the study is defined as "the last visit of the last healthy volunteer undergoing the study".

The study is expected to start and end in Quarter I/2010.

The study may be terminated at individual centres if the study procedures are not being performed according to GCP, or if recruitment is slow. AstraZeneca may also terminate the

entire study prematurely if concerns for safety arise within this study or in any other study with the IPs.

The study will be stopped prematurely if:

- Five or more subjects have adverse events of similar type and of moderate or greater severity not previously reported in $\geq 2\%$ of subjects in Phase 3 clinical trials. Degree of severity will be defined by CTC criteria.
- One serious life threatening adverse event occurs in a cohort that is highly likely to be related to the IMP and unrelated to its mechanism of action.
- Four or more subjects show an unexplained increase in liver enzymes (ALT/AST) ≥ 3 times upper limit of normal in two consecutive samples.
- Data not known before become available and raise concern about the safety of the study drug so that continuation would pose potential risk to the subjects.

10. DATA MANAGEMENT BY ASTRAZENECA OR DELEGATE

10.1 Data collection methods and data validation at study site

10.1.1 Data flow

ClinBase™ system is an electronic source data capturing and information management system. The system combines all aspects of source data capturing with process control and study management. All clinical and laboratory data, except those which are paper based, will be collected by the eSource system ClinBase™. Only paper-based data will be subject to data entry. For electronic data, no data entry will be performed. Data entered on pCRF should be recorded legibly in blue or black ballpoint pen. Correction fluid or covering labels must not be used.

The responsible monitor will check data at the monitoring visits to the study site. The Investigator will ensure that the data collected are accurate, complete and legible. Data will be validated within ClinBase™ by the Investigator and the study monitor before being exported. Any changes made during validation will be documented with a full audit trail within ClinBase™.

designs and builds a database in iVal* to enter the paper-based data for adverse event and concomitant medication. The database and entry screens will be built and validated following a formal, documented verification plan and the system will be tested against the specification for the entry system. The setup will be controlled by test data entry. A standardised setup of Statistical Analysis System (SAS®) data sets in AstraZeneca specification will be done by the SAS® clinical data programmer. Verification of the setup will be performed with dummy and test data.

*The iVal system is a 21 CFR part 11 compliant application ensuring high data quality. The iVal system is a clinical database management system composed of several modules including, but not limited to, a set-up tool, a database designer (data dictionary editor), an entry screen designer (data entry manager), a query manager (iQue), a validation-programming environment, and a SASTM dataset export module (iSAS). For more information refer to the Data Management Plan.

The clinical data manager will develop a data verification specification (DVS) according to the protocol, the data dictionary of the iVal database for paper based-data and the description of the SAS[®] table set for electronic data. Computerised checks to be performed on the data imported or entered into the databases will be defined in this document. The DVS will be sent to AstraZeneca or representative for review and approval.

Paper-based data will be sent to data management and entered into iVal. These data will be exported via the module iSAS later on and merged with the SAS[®] tables in AstraZeneca format. The SAS[®] data sets will be used for verification of the electronic study data following the specifications listed in the DVS. Only trained staff will have access to the databases. Every change will be fully audit-trailed.

The ClinBaseTM data files will be imported into SAS[®] data sets and the imported data checked by the related verification programmes specified in the DVS. Data will be changed only in a controlled, audit-trailed, environment. After these data are considered as clean, they will be mapped into AstraZeneca data structure.

All study related electronic source data captured in ClinBaseTM will be transferred from ClinBaseTM via ClinResult to Data Management after monitoring. These data will be imported into the SAS[®] data sets. Paper based data will be sent to Data Management after they have been monitored. Data Management reviews, logs and files them.

External PK concentration data will be transferred to Data Management as specified by a Bio analytical data transfer specification. This data will be reconciled against the source ClinBaseTM database and any discrepancies will be communicated to the Bio analytical Laboratory.

Any missing, implausible or inconsistent recordings will be referred back to the Investigator using a data query form and be documented for each individual healthy volunteer before clean file status is declared.

The following data will be captured as source electronically using ClinBaseTM:

- Dates and times of all blood and urine samples
- Dates and time of all dosing
- Pulse and BP
- Safety laboratory data

- ECG
- Height
- Weight

10.1.2 Study Data Management Plan (DMP)

The Study Data Management Plan (DMP) will describe the methods used to collect, check and process clinical data in detail. It will also clarify the roles and responsibilities for the different functions and personnel involved in the data management process. Further the DMP will also describe the data flow and timelines within the study.

10.1.3 Coding tools and dictionaries

Adverse events and diagnoses from medical history will be classified according to the terminology of Medical Dictionary for Regulatory Activities (MedDRA). Concomitant medications will be classified according to the WHO Drug Dictionary. All coding will be performed by

11. EVALUATION AND CALCULATION OF VARIABLES BY ASTRAZENECA OR DELEGATE

11.1 Calculation or derivation of safety variables

The closest observation prior to first administration of investigational product will be regarded as baseline.

Change from baseline variables will be calculated as the value minus the value at baseline.

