3.1 Overall study design and flow chart

Table 1 Study Flow Chart

Visit No	Enrolment		Visits for each period *				Follow-up ^a
	1		2 and 3		4	4	
Day No	-19 to -2	-1	1	2	3	4	At least 6 days after last PK sample
Signed Informed Consent Form	X						
In-house		X	X	X	X	X	
Ambulant	X						X
Inclusion/exclusion criteria	X	X					
Demographics	X						
Physical examination	X					X	X
Weight and height ^a	X						X
Medical and surgical history	X						
Serology (HbsAg, HCV Ab, HIV-1/2 Ab)	X						
Urine drug screen	X	X					
Alcohol urine test	X	X					
Vital signs (including body temperature) ^b	X	X	X	X	X	X	X
12-lead ECG	X						X
Safety laboratory (haematology, clinical chemistry, urinalysis)	X	X				X	X
Pregnancy test	X	X					

Table 1 Study Flow Chart

	Enrolment		Visits for each period *				Follow-up ^a
Visit No	1		2 and 3				4
Day No	-19 to -2	-1	1	2	3	4	At least 6 days after last PK sample
Randomisation (Visit 2) ^c			X				
IP administration			X				
PK blood sampling ^d			X	X	X	X	
AE ^e		X	X	X	X	X	X
SAE ^f	X	X	X	X	X	X	X
Concomitant medication	X	X	X	X	X	X	X

Abbreviations: AE = Adverse event; ECG = Electrocardiogram, HBsAg = Hepatitis B surface antigen, HCAb = Hepatitis C antibody, HIV1/2 Ab = human immunodeficiency virus-1/2 antibodies; IP = Investigational product, PK = pharmacokinetic; SAE = Serious adverse event. *The wash-out period will be at least 7 days between the periods.

^a Height will be assessed only at the enrolment visit (Visit 1).

^b Vital signs will be obtained he volunteer in a supine position (resting in bed for at least 10 minutes).

^c Just before dosing

^d Collection of PK blood samples: for the time points visit 2-3 see [Table 2](#).

^e AEs will be recorded from first intake of IP in period 1 until Follow-up.

^f SAEs will be collected from the time when informed consent is obtained until the end of study (including the Follow-up visit).

Table 2 Study plan

Visit	Day	Nominal Protocol Time	IP	PK in Blood	BP pulse	Safety laboratory	Other	
2 and 3	1	pre-dose, -01:00 to -00:30			X			
		-00:30					Start of breakfast	
		-00:05						End of breakfast
		pre-dose			1			
		00:00	X		-			
		00:15			2			

Table 2 Study plan

Visit	Day	Nominal Protocol Time	IP	PK in Blood	BP pulse	Safety laboratory	Other
		00:30		3			
		01:00		4			
		01:30		5			
		02:00		6			
		03:00		7			
		04:00		8			Lunch: not until 4 hours post-dose
		05:00		9			
		06:00		10			
		08:00		11			
		10:00					Dinner
		12:00		12			
		14:00					Sack
		16:00		13			
	2	24:00		14	X		

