5. STUDY CONDUCT

5.1 Restrictions during the study

1. All healthy volunteers will be served standardized meals during the in-house periods at the early phase clinical unit, and no other foods will be permitted. The menus will be identical for visit 2 and 3. Copies of the menu will be provided to the sponsor.
2. On Day 1 of dosing at Visit 2 and 3, the subjects will fast for 8 hours overnight. Breakfast will be served 30 minutes prior to dosing of each subjects medication.
3. The pre-dose meal should be a standardized non-high fat meal (650 calories with about 30% of calories derived from fat). The composition of the meal should be described with regard to protein, carbohydrate, and fat content (specified in grams, calories and relative caloric content).
4. Water will be allowed ad lib except from 2 hours before until 2 hours after dose administration.
5. The drug product should be dosed with 240 mL of room temperature water.
6. Eat and drink only the standardised meals and drinks provided (apart from water) during the residential period in the unit.
7. Abstain from consuming any of the following.
8. Drugs of abuse during the entire study. In addition, poppy seeds (eg, on bread rolls) can give a positive signal for opiates and should not be ingested 72 hours before screening (Visit 1) until the end of the study.
9. Food and drink (except water) for at least 8 hours prior to safety laboratory measurements at screening (Visit 1) and follow-up (Visit 4).
10. Consuming grapefruit, grapefruit juice Seville oranges, or orange marmalade (made with Seville oranges) or other products containing grapefruit or Seville oranges beginning 7 days before screening (Visit 1) and during the study.
11. Liquorice containing products 24 hours prior to admission and during Visit 2 and 3. Alcohol from 72 hours before and during enrolment (Visits 1) and before admission and during Visit 2.

12. Caffeine-containing beverages and foods, eg, coffee, tea, chocolate, and soft drinks (eg, Red Bull) for 10 hours before drug administration.
13. Abstain from nicotine use and smoking throughout the entire study period until after the final medical examination at the study follow-up.

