5.5.2 Doses and treatment regimens

The following doses will be administered in one of two fixed order sequences according to a randomization schedule:

Sequence 1 will administer the FDC in period 1 and the free combination in period 2.

Sequence 2 will administer the treatments in the reverse order. For Part II, subjects will be randomized in the same way as in Part I.

All doses will be orally administered as single doses. The tablets should be swallowed together with 240 mL distilled water, the subject in upright position, in the morning of Day 1 of both treatment periods in both study parts. Investigational products administration will be supervised by study staff and will be followed by a mouth check.

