12.2.4 Safety and tolerability

Continuous variables will be summarised using descriptive statistics (n, mean, SD, min, median, max) by treatment group. Categorical variables will be summarised in frequency tables (frequency and proportion) by treatment group. Graphical presentations will be used as appropriate. Examples include shift plots showing pre-treatment values on the horizontal axis and post-treatment values on the vertical axis.

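### Section 11.1 sets one baseline, before the Period 1 dose, for both crossover periods, so Period 2 safety changes include drift that arose before the Period 2 treatment

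*Protocol*

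**What the plan says.** Protocol Section 11.1 gives one baseline rule for the safety variables: "The closest observation prior to first administration of investigational product will be regarded as baseline". The change score follows from it: "Change from baseline variables will be calculated as the value minus the value at baseline". No section defines a separate baseline for Period 2.

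Section 12.2.4 summarises continuous and categorical safety data by treatment group. On graphics it says: "Examples include shift plots showing pre-treatment values on the horizontal axis and post-treatment values on the vertical axis". It does not say which period's pre-treatment value is meant. Sections 12.2.4.3 and 12.2.4.4 leave further detail on laboratory variables and vital signs to a separate SAP.

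In Section 3.1, Table 1 schedules safety laboratory tests and vital signs on Day -1, and again on Day 4. Table 2, which applies to Visits 2 and 3, adds a blood pressure and pulse measurement at "pre-dose, -01:00 to -00:30" on Day 1. ECG is recorded only at enrolment and follow-up.

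**The concern.** In a two-period crossover, a change tabulated under a treatment should start from the state just before that treatment. Under Section 11.1 it does so only in Period 1. In Period 2 the starting value predates the other treatment, a full set of pharmacokinetic blood draws and the wash-out. Whatever moved in between is reported under the treatment given second.

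What is at stake is the secondary objective, safety and tolerability. A haemoglobin fall or a transaminase rise that was already present before the Period 2 dose would appear as a change or shift under the Period 2 treatment. The values needed to separate the two are already being collected.

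**Working it through.** **1. Which dose is the first administration?** Section 5.5.2 states "All doses will be orally administered as single doses", one in each period. A footnote to Table 1 uses the same idea explicitly: "AEs will be recorded from first intake of IP in period 1 until Follow-up". Baseline is therefore the last value before the Period 1 dose.

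**2. Are pre-dose laboratory values taken in both periods?** Table 4 (Section 7.1) gives 6 clinical chemistry and 6 haematology samples per volunteer. From Table 1:

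- Day -1 in both periods: 1 (enrolment) + 2 × 2 (Day -1 and Day 4) + 1 (follow-up) = 6, which reproduces Table 4.
- Day -1 in one period only: 1 + 1 + 2 + 1 = 5, which does not.

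Section 6.3.5 agrees. It places the serum pregnancy test at Visits 1, 2 and 3, and the note to Table 4 says this test is run on the clinical chemistry sample.

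**3. What does a Period 2 change contain?** Write P1pre and P2pre for the pre-dose values in each period, and P2post for a Period 2 post-dose value.

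P2post − P1pre = (P2post − P2pre) + (P2pre − P1pre)

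The second bracket was complete before the Period 2 dose. With a period-specific baseline it drops out.

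**4. The part that can be sized from the protocol: blood drawn.** Inputs are 21 PK time points per period (Table 2), 6 mL per time point (4 mL + 2 mL, Section 6.4.1), chemistry 7.5 mL, haematology 2.7 mL and the tricyclic antidepressant sample 1.1 mL (Table 4; its three samples are taken to fall at screening and the two admissions).

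- PK per period: 21 × 6 = 126 mL.
- After the Period 1 Day -1 sample and before the Period 2 Day -1 sample: 126 + 7.5 + 2.7 = 136.2 mL. Counting the Period 1 Day -1 draw itself (7.5 + 2.7 + 1.1 = 11.3 mL), it is 147.5 mL.
- From the Period 2 Day -1 draw to the Period 2 Day 4 sample: 11.3 + 126 = 137.3 mL.
- Span of a Period 2 Day 4 change under Section 11.1: 136.2 + 137.3 = 273.5 mL.

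The protocol gives no blood volume. For an assumed 4, 5 or 6 L, 136.2 mL is 3.4%, 2.7% or 2.3%.

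**5. Effect on treatment summaries.** Let c be the offset P2pre − P1pre, with 30 volunteers per sequence in each part.

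| Situation | Shift in FDC mean | Shift in free-combination mean | Shift in difference |
|---|---|---|---|
| Same c after both treatments, 30/30 | c/2 | c/2 | 0 |
| c only after the FDC | 0 | c/2 | c/2 in size |
| Same c; 3 volunteers per sequence miss Period 2 | 27c/57 | 27c/57 | 0 |
| Same c; all 6 anticipated non-completers from the sequence with the FDC second | 24c/54 = 0.44c | 30c/60 = 0.50c | about 0.06c in size |

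In every row with the same c, an individual's Period 2 change is off by the full c.

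**The case against.** The strongest reply is that a single unexposed baseline is a legitimate choice. The secondary objective concerns the combination of the two drugs, not a safety contrast between formulations, and both arms deliver the same substances at the same doses. Cumulative change from the drug-free state is then a coherent quantity. A per-period baseline also has a cost: an abnormality that begins in Period 1 and persists becomes the Period 2 baseline and disappears from the Period 2 change. That part stands, and the fix has to keep a cumulative display. It does not rescue the rule as written, because results are reported by treatment group and half of the changes so labelled start before the other treatment.

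Second, Section 12.2.4 does not tie its shift plots to the Section 11.1 baseline, and presentation details are left to an SAP that is not shown. Out-of-range tables and plain listings do not depend on baseline at all. This narrows the reach of the point. But Section 11.1 states the rule outright, and an SAP using period baselines would depart from it.

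Three stronger readings are tempting and are not supported:

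- A reader might infer that the comparison of the two formulations is biased. The blood draw is the same after either treatment, and equal dropout leaves the difference unchanged. Even the most lopsided allocation of the six non-completers moves it by only about 0.06c. A c/2 bias would need an offset that follows one treatment only, and nothing in the protocol shows one.
- A reader might convert the blood volume into an expected haemoglobin fall. That needs an assumed blood volume, an assumed starting haemoglobin and no recovery over a wash-out of at least 7 days. Residual drug effect at the Period 2 pre-dose point cannot be sized, since no half-life is given.
- Section 5.1 requires an 8-hour fast before safety laboratory tests only at Visits 1 and 4, and a reader might count this as further evidence. It is a separate matter affecting glucose, it is not quantified, and a period baseline would not settle it.

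**Conclusion.** The point holds, at low severity. As written, Section 11.1 measures Period 2 safety changes from a value taken before Period 1 treatment, although Period 2 pre-dose laboratory values and vital signs are available. The offset includes about 136 mL of Period 1 blood draw, 2.3 to 3.4% of an assumed 4 to 6 L; for that volume the percentage is an upper bound on dilution because recovery is ignored. It distorts absolute by-treatment changes (by c/2 on average with full, balanced sequences) and individual Period 2 shifts (by c).

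The between-treatment mean difference is essentially unaffected if the sequences are balanced and the offset is the same after both treatments. The safety analysis is descriptive. The liver stopping criterion in Section 9.5 uses multiples of the upper limit of normal rather than change from baseline, and the primary bioequivalence analysis in Section 12.2.3 does not use this baseline. A reader should not infer any threat to the study's main conclusion.

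**What to change.** Replace the baseline sentence in Section 11.1 with wording such as:

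*For laboratory variables and vital signs, baseline for each period is the last observation before dosing in that period, and is used for that period's by-treatment changes and shift plots. The last observation before the Period 1 dose (for ECG, the enrolment recording) is the reference for the follow-up visit and for a listing of cumulative change.*

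State in Section 12.2.4 that the pre-treatment values in the shift plots are those of the same period. The cumulative listing keeps a persistent Period 1 abnormality visible.

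The cost is one extra derivation flag and one listing. No added samples or visits are needed, because the pre-dose observations are already scheduled in both periods.
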